Treatment dispensing / accountability			X	←=====→									
AE review ^b			←=====→										
AEs of interest review, including fall ^c			←=====→										
Timed Up and Go assessment (TUG) ^d	X ^h		X ^h			X	X		X	X			
Short Physical Performance Battery (SPPB) ^d			X			X	X		X	X			
Accelerometry assessment ^e	X					X	X		X	X			
Cognitive function ^f			X				X		X	X			
Brief Fatigue Inventory (BFI) ^g			X	X	X	X	X		X				
Patient Health Questionnaire (PHQ-9)			X	X	X	X	X		X	X			
Survival status												X	

X = measure/action to be performed at the time point indicated

←=====→ = measure/action to be performed continually during the time period indicated

AE = adverse event; BFI = Brief Fatigue Inventory; COWA = Controlled Oral Word Association; CRF = case report form; HVLTR = Hopkins Verbal Learning Test - Revised; PHQ-9 = Patient health questionnaire-9; PSA = prostate-specific antigen; SPPB = Short Physical Performance Battery; TMT = Trail Making Test; TUG = Timed Up and Go

- a PSA will be assessed at the same time as other laboratory assessments. A time window of ± 14 days is allowed for laboratory and PSA assessments.
- b Including survival, pain, radiographic progression, metastases, and skeletal events
- c AEs of interest are fractures, falls, and hypothyroidism
- d Physical function tests include SPPB and the TUG assessment.
- e Accelerometry assessment will require the participant to wear an accelerometry device on the wrist or hip for a minimum of 7 days at each time point. The first accelerometry assessment is to be performed before the first dose (i.e. during screening).
- f Cognitive function tests include the HVLTR, TMT, and COWA, as well as the patient-reported outcome questionnaire FACT-Cog.
- g BFI is a 5 minute self-assessment tool that identifies fatigue in cancer participants over a 24-hour period.
- h The first TUG assessment is to be performed before the first dose (either during screening or Week 1 Day 1).
- i Once the baseline procedures are completed, the first administration of study intervention will be provided at the study center and the participant will be provided with additional medication to take as scheduled through the Week 4 visit. (Each participant will be instructed to bring any remaining drug back to the center at the Week 4 visit.)

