8.2 Safety Assessments

Planned time points for all safety assessments are provided in the SoA in Section 1.3.

Safety assessments in this study are AEs, as recorded by the investigator. Descriptive summary tables will be presented for all safety parameters by each treatment arm.

All AEs will be coded using the Medical Dictionary for Regulatory Activities (MedDRA) coding system and graded using NCI-CTCAE version 5.0. A TEAE is defined as any event arising or worsening after start of study drug administration until 30 days after the last study drug intake.

Fatigue, cognitive function and depression will be assessed as described below.

Other AEs of interest including fractures, falls, fractures, and hypothyroidism will be collected with specific questions on CRF.

Study assessments for physical ability and cognitive function are described in [Table 8–1](#).

Table 8–1: Study Assessments for Physical Ability and Cognitive Function

Test	Description	Possible range of score	MCID / RCI from baseline
Physical ability tests			
Timed Up & Go (TUG)	The TUG test is used to assess a person's mobility and requires both static and dynamic balance. It uses the time that a person takes to rise from a chair, walk three meters, turn around, walk back to the chair, and sit down. Where possible, TUG time is to be measured by independent blinded assessors.	>1second	1 second (Davies et al. 2016)
Short Physical Performance Battery (SPPB)	The SPPB is a group of measures that combines the results of the gait speed, chair stand and balance tests.	0–12 points	0.5 points (Davies et al. 2016)
Cognitive Tests			
Hopkins Verbal Learning Test-Revised Total Recall (HVLTR TR)	The HVLTR is a learning and memory test, in which the participant is asked to learn and recall a list of 12 words over 3 trials.	0–36 words	±5 words (Wefel et al. 2011)
Hopkins Verbal Learning Test-Revised Delayed Recall (HVLTR DR)	Spontaneous recall is assessed before and after a delay.	0–12 words	±3 words (Wefel et al. 2011)
Hopkins Verbal Learning Test-Revised Delayed Recognition (HVLTR RECOG)	Recognition discriminability is also assessed after a delay. Four alternate versions of the test are used to minimize practice effects over time.	-12–+12 words	±2 words (Wefel et al. 2011)

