9.4.2 Safety Analyses

All safety analyses will be performed on the Safety population.

Endpoints measuring physical function, cognitive function, and daily activity will also be performed on the Safety population.

Endpoint	Statistical Analysis Methods
Primary	
The primary variable in this study is the proportion of participants with a worsening in TUG time during the 24-week period from baseline. Worsening is defined as an increase of at least 1 second in TUG time from baseline by 24 weeks.
 
 At each assessment, change in TUG test time (seconds) from baseline will be calculated, and the status will be categorized as: improved, stable, or declined using the MCID of 1 second. Decline in physical function is defined as at least a 1-second increase from baseline in TUG time in each arm by 24 weeks. The proportion of participants with a decline and the 95% CIs will be summarized for each treatment arm. This rate will be compared between the two arms using Cochran-Mantel-Haenszel test adjusting for stratification factors as captured by IWRS.

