## 2.0 Objectives and Endpoints

**Table 1 Objectives and Endpoints**

Objectives	Endpoints
Primary	

The primary objective of this study is to compare the effects of treatment with darolutamide vs. enzalutamide on physical function as assessed by the Timed Up and Go (TUG) test in participants with castration-resistant prostate cancer (CRPC).
	
Proportion of participants with a worsening in TUG time during the 24-week period from baseline. Worsening is defined as an increase of at least 1 second from baseline, using the best TUG time out of the measured assessments during study visits. (The minimum clinically important difference [MCID] in TUG time is 1 second (Davies et al. 2016)) [1].

Secondary	

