#### 5.1.1 Definitions

**Baseline:** The last measurements taken prior to first exposure to study drug, including Day 1 measurements taken pre-dosing. If patients have no value as defined above for a particular parameter, the baseline value will be missing.

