### 5.5.1 Primary Endpoint Analyses

The primary variable in this study is the proportion of participants with a worsening in TUG time during the 24-week period from baseline, using the best TUG time out of the measured assessments during study visits (two or

three assessments). Worsening is defined as an increase of at least 1 second in TUG time from baseline.

The proportion of participants with a worsening in TUG time and the (exact) 95% CIs will be summarized by treatment arm. A comparison between treatment arms will be made using Cochran-Mantel-Haenszel (CMH) test adjusting for Age (<75, ≥75). A sensitivity analysis will be provided by replacing missing TUG times with ≥ 1 second increase. Primary endpoint (worsening in TUG) analysis will be performed by age (<75, ≥75), metastatic state (nmCRPC, mCRPC), Pain (yes, no pain), and opioid use (yes, no opioid use). Information on pain and opioid use will be retrieved from an examination of medical history and prior medication CRFs.

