## **6.0 Changes to Planned Analyses**

Not applicable.

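### The TUG score is the best of two or three trials, but neither document fixes the number or matches it between baseline and follow-up, so unequal counts shift the 1-second worsening rate

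*SAP*

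**What the plan says.** SAP 5.5.1 defines the primary variable "using the best TUG time out of the measured assessments during study visits (two or", continuing "three assessments). Worsening is defined as an increase of at least 1 second in TUG time from baseline". SAP Table 1 repeats the rule without a count: "Worsening is defined as an increase of at least 1 second from baseline, using the best TUG time out of the measured assessments during study". Neither document says when two trials are run and when three, or asks for the same number at each visit.

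The general baseline rule in SAP 5.1.1 is "The last measurements taken prior to first exposure to study drug, including Day 1 measurements taken pre-dosing". It does not say how that combines with a best-of score. Footnote h to the protocol's schedule of activities allows two pre-dose occasions: "The first TUG assessment is to be performed before the first dose (either during screening or Week 1 Day 1").

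The protocol has no best-of rule. Its section 9.4.2 says only "Worsening is defined as an increase of at least 1 second in TUG time from baseline by 24 weeks". SAP 6.0, on changes to planned analyses, reads "Not applicable".

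Treatment is open label. On TUG assessors, protocol Table 8–1 says "Where possible, TUG time is to be measured by independent blinded assessors". The one TUG sensitivity analysis in the SAP replaces missing times and does not address the number of trials.

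**The concern.** The fastest of several attempts gets faster, on average, as attempts are added. Best-of-two and best-of-three times are therefore on slightly different scales, and a change from one to the other contains a shift unrelated to function. The endpoint is cut at a hard 1-second threshold, so a shift of a few tenths of a second reclassifies participants near the cut.

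The lead-in phase is most directly exposed. It has no control arm, and its TUG worsening rate is among the results used to choose the endpoint and reassess the sample size (protocol 4.1 and 9.2; SAP 3.1 and 3.4). In the randomized phase the question is whether a mismatch would be the same in both arms.

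The best-of rule is also an addition to the protocol definition that SAP 6.0 does not record. That part needs no numerical assumption.

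**Working it through.** **1. The plan's own power figure.** Inputs from protocol 9.2 and SAP 3.4: worsening 20% vs 40%, one-sided alpha 10%, about 120 randomized 1:1, 10% drop-out. Evaluable per arm: 60 × 0.9 = 54.

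Power = Φ[(Δ − z₀.₉₀ √(2p̄(1−p̄)/n)) / √((p₁(1−p₁)+p₂(1−p₂))/n)]
= Φ[(0.20 − 1.2816 × √(0.42/54)) / √(0.40/54)]
= Φ[(0.20 − 0.1130)/0.0861] = Φ(1.01) = 84.4%.

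The stated 85% reproduces.

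**2. Mean shift from one extra trial.** For independent normal trials with within-session SD s, the expected minimum is −s/√π = −0.564s for two trials and −3s/(2√π) = −0.846s for three. The difference is 0.282s: 0.08 s at s = 0.3, 0.14 s at s = 0.5 and 0.28 s at s = 1.0, against a threshold of 1 s. The documents do not give s, so the range is an assumption.

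**3. Effect on the endpoint as defined.** Change at a visit = true change + min(follow-up trial errors) − min(baseline trial errors). Worsening = change of at least 1 s at Week 12 or Week 24, the two post-baseline TUG visits in the 24-week window. Assumed: true change normal with mean 0 and SD 1 s, correlation 0.5 between visits. Simulated percentages, by trials at baseline/follow-up:

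| s (seconds) | 2/2 | 3/3 | 2/3 | 3/2 |
|---|---|---|---|---|
| 0.3 | 27.4 | 27.1 | 24.4 | 30.3 |
| 0.5 | 30.4 | 29.6 | 25.4 | 34.9 |
| 0.8 | 35.5 | 34.2 | 28.2 | 42.2 |
| 1.0 | 38.8 | 37.2 | 30.2 | 46.5 |

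The smallest shift from 2/2 is 30.3 − 27.4 = 2.9 points and the largest is 38.8 − 30.2 = 8.6. These apply if every participant is mismatched the same way. If half are, and mismatch is unrelated to true change, the shift halves: at s = 0.5 for 2/3, 0.5 × 5.0 = 2.5 points. Equal counts differ by 0.3 to 1.6 points.

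**4. Calibrated to the plan's rates.** The mean change is now set so that 2/2 gives 20% or 40%, with SD of true change 0.8 s and correlation 0.5:

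| s (seconds) | 20% becomes (2/3; 3/2) | 40% becomes (2/3; 3/2) |
|---|---|---|
| 0.3 | 16.9; 22.8 | 35.7; 44.0 |
| 0.5 | 15.3; 24.2 | 33.5; 46.0 |
| 1.0 | 13.3; 25.8 | 30.5; 48.6 |

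With SD of true change 1.5 s the shifts are about 2 to 7 points.

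**5. Power and type I error.** These use the rates of step 4 at s = 0.5, with 54 per arm.

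- Same mismatch in both arms: power is 82.7% (2/3) or 86.9% (3/2), against 84.4%. With 3/3 throughout it is 85.5%.
- Hypothetical extreme, one whole arm mismatched: 2/3 in the enzalutamide arm only cuts power to 62%. With no true difference (40% in each arm), 2/3 in the darolutamide arm only raises one-sided rejection from 10% to about 28% (21% at s = 0.3, 40% at s = 1.0).

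**The case against.** The strongest reply is that the count may be fixed outside these documents. SAP 1.1 lists annotated eCRFs among its sources, and these could set the number of trials or the condition for a third. That is possible, but the SAP itself allows two or three, so its derivation has to deal with unequal counts.

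The within-visit reading is likely but not certain, because SAP 5.5.2 also uses the word assessment at visit level. If another meaning was intended, the wording still needs correcting.

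For a lead-in of 30, sampling error is larger than the shift: protocol Table 9–1 gives 7.71% to 38.57% around an observed 20%. That is fair on proportion, but the shift is systematic and costs almost nothing to remove.

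A reader might infer three stronger things that the documents do not support:

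- **That sites choose the count, or add a third attempt after a slow second.** Neither document says who sets the number. Open-label treatment and conditional blinding leave this possible and no more.
- **That baseline is a single last trial set against a best-of-three.** SAP 5.1.1 speaks of measurements in the plural, which can cover the whole set at the last pre-dose visit, and the best-of rule does not exclude baseline.
- **That the gap between the 3/2 and 2/3 rates can be set against the 20-point effect.** That gap contrasts two universal and opposite mismatches, whereas 20 points is a difference between arms. Nothing suggests that the arms would split that way.

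The randomized-phase endpoint is also still to be confirmed after the lead-in, so any effect there is conditional on that choice.

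**Conclusion.** The point holds as a defect in the scoring rule. The rule as written can compare a best-of-two with a best-of-three, and the direction of the resulting shift is certain. Its size is not: it rests on an assumed within-session SD of 0.3 to 1.0 s, independent normal trials, and the assumed distribution of true change. On those assumptions the 24-week worsening rate moves by about 3 to 9 points under universal mismatch in one direction, and by proportionately less under partial mismatch. The number of trials itself matters little; inequality between visits is what matters.

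The firm consequence is for the uncontrolled lead-in rate. A mismatch shared by both arms leaves power close to the plan. Bias in the randomized comparison needs counts that differ by arm, which the documents neither show nor exclude, so the one-arm figures in the working show sensitivity and do not predict what will happen. Separately, the best-of rule departs from the protocol definition and is not declared. The change should be made, but it does not call the design into question.

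**What to change.** In SAP 5.5.1 and Table 1:

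- State that the assessments are repeat trials within a visit, if that is what is meant.
- Score TUG at every visit, baseline included, as the best of the first two recorded trials. Using recorded trials avoids a judgement about which ones are valid.
- State that the TUG baseline is this score at the last pre-dose TUG visit, so that it takes precedence over the general rule in SAP 5.1.1.
- Report the best of all recorded trials as a sensitivity analysis.

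In SAP 6.0, list the best-of rule as a change from the protocol.

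This costs a few sentences and a small change in derivation code, with no new data. Third trials drop out of the primary score but still inform the sensitivity analysis. The sample-size case is unaffected, because with matched counts power stays at 84.4% (2/2) to 85.5% (3/3).

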### 3.3 Randomization and Stratification

Following the primary evaluation of the lead-in phase, approximately 120 additional patients will be randomized in a 1:1 ratio to receive either darolutamide (600 mg twice daily) or enzalutamide (160 mg once daily) using an Interactive Web Response System. Randomization will be stratified by age (<75, ≥75 years).

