## Randomized phase

The sample size calculation for the randomized phase of the study is based on the primary endpoint of physical decline (using TUG test as an example). In the event that the primary endpoint or the assumed rate of decline changes based on results from the lead-in phase of the study, the sample size will be adjusted accordingly.

Approximately 120 participants in the randomized phase of the study will provide 85% power to detect a difference of 20% in the two arms using one-sided alpha of 10%. This is assuming that 20% of participants in the darolutamide arm and 40% of participants in the enzalutamide arm will have a worsening in physical function at 24 weeks as measured by the TUG test. Worsening is defined as an increase of at least 1 second in TUG time from baseline. A 10% drop-out rate is assumed.

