## **5.5.2 Secondary Endpoints Analyses**

### **Physical function**

- Proportion of participants with a worsening in TUG time from baseline at 12 and 24 week study visits, and at any time up to 52 weeks will be summarized.
- TUG time (secs) and percent change from baseline will also be summarized by metastatic/non-metastatic CRPC status, pain (yes, no pain), and opioid use (yes, no opioid use).
- At each assessment, status of TUG time will be summarized as the categories of improved, stable or worsened.
- Time to worsening in TUG time will be defined as time from randomization (or time from first dose for participants in the lead-in phase) to the first date a participant had a worsening. Time to worsening in TUG time will be summarized using Kaplan-Meier methodology, and a comparison between the two arms in the randomization phase will be made using a two-sided, stratified log-rank test, stratified by Age (<75, ≥75). The hazard ratio as well as its 95% CI will be presented using a stratified Cox regression model. An unstratified analysis will also be performed. The Kaplan-Meier plots will be provided for both stratified and unstratified analyses.
- Similar to the primary endpoint, the proportion of participants with a decline of at least 1 point in SPPB total score at 12 and 24 week study visits and at any time up to 24 and 52 weeks will be summarized. SPPB

will be analyzed by age (<75, ≥75), metastatic state (nmCRPC, mCRPC), Pain (yes, no pain), opioid use (yes, no opioid use).

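### The randomized-phase TUG and SPPB subgroup analyses plan no estimate of whether the treatment effect differs between subgroups, so a chance contrast in at least one of the four factors is likely

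*SAP*

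**What the plan says.** SAP 5.5.1 defines the primary analysis as the proportion of participants whose TUG time worsens, with exact 95% CIs by arm, and an arm comparison by CMH test adjusted for age. It then adds a subgroup instruction: "Primary endpoint (worsening in TUG) analysis will be performed by age", metastatic state, pain and opioid use. That is four binary factors, so eight subgroups. SAP 5.5.2 (Physical function) introduces the SPPB proportions as similar to the primary endpoint and says SPPB "will be analyzed by age (<75, ≥75), metastatic state (nmCRPC, mCRPC), Pain (yes, no pain), opioid use".

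I found no treatment-by-factor term, homogeneity test, minimum subgroup size, multiplicity rule or exploratory label for these analyses in either document. Randomization is stratified by age only (SAP 3.3).

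The study is sized for the overall comparison alone (SAP 3.4): "Approximately 120 participants in the randomized phase of the study will provide 85% power" for a 20-point difference at one-sided 10%. The planning rates are worsening in 20% on darolutamide and 40% on enzalutamide, and the same section adds: "A 10% drop-out rate is assumed".

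**The concern.** Whether a treatment works differently in two groups is a question about the difference between two effects. Separate analyses in each level do not answer it. One level can be significant and the other not when the true effect is the same in both, because each has only part of the sample and limited power.

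At stake is the interpretation of the randomized phase. A statement that darolutamide preserves mobility in one kind of patient but not in another could rest on nothing more than two underpowered comparisons falling on opposite sides of a threshold. With four factors examined, there are four chances for that to happen.

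**Working it through.** **Inputs from the documents (SAP 3.3 and 3.4).** About 120 randomized 1:1; 10% drop-out, so 120 × 0.9 = 108 evaluable, 54 per arm; worsening in 20% versus 40%; one-sided alpha 10% (z = 1.2816).

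**Assumptions, because the documents are silent.** Each factor splits the sample evenly; the four factors are independent; the effect is 20% versus 40% in every subgroup; subgroup tests use the same one-sided 10%; a pooled two-proportion z-test stands in for the CMH test.

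**Step 1: reproduce the plan's power.** Power = Φ{[d − z·√(2·p̄(1−p̄)/n)] / √[(p₁(1−p₁)+p₂(1−p₂))/n]}, with d = 0.20 and p̄ = 0.30. For n = 54: √(0.42/54) = 0.0882 and √(0.40/54) = 0.0861. Then (0.20 − 1.2816 × 0.0882)/0.0861 = 1.01, so power is 84.4%. The stated 85% is reproduced.

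**Step 2: power within one level.** At an even split n = 27 per arm: √(0.42/27) = 0.1247 and √(0.40/27) = 0.1217. Then (0.20 − 1.2816 × 0.1247)/0.1217 = 0.33, so power is 62.9%.

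**Step 3: one named factor.** With q the power in each level:
- exactly one level significant: q₁(1−q₂) + q₂(1−q₁) = 2 × 0.629 × 0.371 = 46.7%
- both significant: 0.629² = 39.6%
- neither significant: 0.371², about 14%
- one pre-named level significant and the other not: 0.629 × 0.371, about 23%

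**Step 4: at least one of four factors.** Treating the factors as separate experiments would give 1 − 0.533⁴, about 92%. That is too high, because the same men and outcomes are re-divided four times. In 40,000 simulated trials, each with one shared set of outcomes, at least one factor was discordant in about 77%.

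**Step 5: sensitivity to split and alpha.** Chance that one factor is significant in exactly one level, 54 evaluable per arm:

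| Split | One-sided 10% | Two-sided 5% |
|---|---|---|
| 50/50 | 46.7% | 45.9% |
| 60/40 | 47.7% | 46.6% |
| 70/30 | 50.8% | 48.6% |
| 80/20 | 56.0% | 51.9% |
| 90/10 | 63.7% | 56.2% |

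For at least one of four factors at two-sided 5%, the even-split figure is again about 77%. At one-sided 10%, independent factors with assumed shares of 40/50/30/20% give 83%. More varied uneven splits, with opioid use nested within pain, give 81% to 90% (about 77% at two-sided 5%).

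**Step 6: what the proper contrast could show.** The difference between the two risk differences at an even split has SE = √[2 × (0.24 + 0.16)/27] = 0.172. The 95% half-width is 1.96 × 0.172 = 0.337, about ±34 points.

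**The case against.** The strongest reply is that the SAP never says it will report a subgroup p-value. SAP 5.1 applies every analysis to both phases unless stated otherwise. In the single-arm lead-in, the same sentence can only mean descriptive proportions. The lead-in output index (SAP 9.0) lists TUG by metastatic status with no comparison. No claim or decision is tied to a subgroup, and the endpoint and sample size are to be reconsidered after the lead-in.

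Part of this stands. The issue is confined to the randomized phase, and subgroup testing is an inference. It is a fair one: SAP 5.5.1 says the primary analysis itself is performed by factor, and that analysis includes the CMH comparison. Elsewhere the SAP uses weaker verbs: TUG time and percent change are summarized by subgroup (5.5.2), and PSA progression and survival are explored across subgroups (5.4.3). If only proportions were produced, a planned estimate of effect difference would still be missing.

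Three stronger readings are tempting, and the documents do not support them:
- **That a given factor will usually show a false contrast.** With equal power in both levels the chance cannot exceed 50%, and here it is about 47%. It passes 50% only at about 70/30 or more uneven (one-sided 10%) or about 80/20 (two-sided 5%), and no shares are given. The 77% refers to any of the four factors.
- **That a specific claim, such as benefit in non-metastatic but not metastatic disease, is a likely artefact.** One factor in one direction has a chance of about 23% at an even split.
- **That readers could compare only significance labels.** If the primary analysis is repeated by level, arm-specific proportions with exact CIs come with it, and a reader could derive the risk differences and their contrast. What is absent is a planned and reported estimate.

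**Conclusion.** The point holds in limited form. For the randomized phase, the SAP repeats the primary TUG analysis by four factors (and SPPB similarly) without planning any estimate of how the effect differs between levels. Under a uniform 20% versus 40% effect, a pattern of significance in one level only arises in about 47% of trials for any one named factor and about 77% for at least one of the four. The arm size and event rates come from the SAP. Even splits, independent factors and the subgroup alpha are assumptions. Independence is doubtful for pain and opioid use, but nesting one in the other, with uneven splits, left the any-of-four figure at about 77% or higher. Severity is low: the overall primary comparison is untouched, and only the reading of the subgroup tables is exposed.

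**What to change.** In SAP 5.5.1, and for SPPB in 5.5.2, specify for the randomized phase that each factor is reported as the arm difference with 95% CI in each level, plus the treatment-by-factor estimate: the difference between the two risk differences with 95% CI, or a logistic interaction term. Label these analyses exploratory, and state that differences in effect are read only from that estimate and not from within-subgroup p-values.

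The cost is a short SAP amendment and one extra model term per factor for each endpoint. The SAP already plans a model containing all four factors for accelerometer counts (5.5.2, Daily Activity). The drawback is the wide interval. The change guards against over-reading and adds no power to detect real heterogeneity.
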